### 4.4. Duration of Treatment

All subjects will receive their randomized treatment in a blinded manner for up to 96 weeks. Following completion of the assigned treatment, all subjects will continue to receive NrtI during the 24-week follow-up period. Following completion of the 24-week follow-up period, subjects will exit the study and resume standard of care oversight by their physicians.

## 5. POPULATION

### 5.1. Number of Subjects

Approximately 40 male or female subjects between the ages of 18 and 65 will be enrolled in the study. Subjects will have HBeAg positive or negative CHB, no evidence of cirrhosis or end-stage liver disease and will not be adequately suppressed on NrtI therapy.

### 5.2. Inclusion Criteria

Subjects must meet all of the following inclusion criteria in order to be eligible for enrollment:

1. Willing and able to provide informed consent
2. Male or female between the ages 18 and 65 years (inclusive)
3. Body mass index (BMI) 18 to 36 kg/m^2 and a minimum body weight of 45 kg (inclusive)
4. Female subjects of child-bearing potential ([Appendix 4](#)) must be non-pregnant and have a negative serum pregnancy test at Screening and a negative urine pregnancy test predose on Day 1.
5. HBeAg positive or HBeAg negative CHB Chronic hepatitis B infection, defined as HBV infection documented for  $\geq 12$  months.
6. HBV DNA  $>LLOQ$  (using a commercially available assay with  $LLOQ=20$  IU/mL) from 2 samples drawn on 2 separate occasions during the Screening period approximately 10-14 days apart. If the results from these 2 samples indicate a decline in HBV DNA then a third sample will be collected at least a week later for Sponsor review and approval prior to randomization.
7. On a stable NrtI regimen (ETV, TDF, or TAF) for more than 12 months, without evidence of resistance and while known to be adherent to therapy
8. Lack of cirrhosis or advanced liver disease as documented by the following:
  - Liver biopsy results of METAVIR F0-F3 (absence of cirrhosis) within 1 year of Screening
  - OR
  - Fasting FibroScan®  $\leq 14$  kPa within 3 months of Screening (including the Screening visit) or other Sponsor-approved hepatic imaging method within 6 months of Screening indicating lack of cirrhosis (F0 to F3 or equivalent).

If the results from both liver biopsy and FibroScan are available, then the diagnostic method reporting the most advanced liver disease will be used to determine eligibility for the study.
9. Agreement to comply with protocol-specified contraceptive requirements (Refer to [Appendix 4](#)).
10. Agreement to abstain from alcohol abuse (defined as alcohol consumption exceeding 2 standard drinks per day on average (1 standard drink=14 grams of alcohol) and the use of illicit substances from Screening through the duration of the study

11. In good general health, except for CHB (in the opinion of the Investigator)
12. Have the ability to take oral medication and, in the opinion of the Investigator, be willing to adhere to study treatment

### 5.3. Exclusion Criteria

Subjects who meet **any** of the following exclusion criteria will not be eligible for the study:

1. Current or prior treatment for CHB with
  - Lamivudine, telbivudine or adefovir (any duration)
  - HBV core inhibitor (any duration)
  - Previous treatment with an investigational agent for HBV infection
2. Presence of substitutions in the HBV polymerase coding region which may confer reduced susceptibility to NrtIs ([Appendix 2](#))
3. Co-infection with human immunodeficiency virus (HIV), hepatitis A virus (HAV) hepatitis C virus (HCV), hepatitis E virus (HEV), or hepatitis D virus (HDV)
4. Females who are lactating, or wish to become pregnant during the course of the study
5. History or evidence of advanced liver disease or hepatic decompensation (including jaundice, ascites, portal hypertension, gastrointestinal bleeding esophageal varices, hepatic encephalopathy,) at any time prior to, or at the time of Screening
6. History of persistent alcohol abuse (alcohol consumption exceeding 2 standard drinks per day on average [1 standard drink=14 grams of alcohol]) or illicit drug abuse within 3 years prior to Screening
7. Clinically significant diseases or conditions, such as cardiac disease including poorly controlled or unstable hypertension; pulmonary disease; chronic or recurrent renal or urinary tract disease; liver disease other than CHB; endocrine disorder; autoimmune disorder; poorly controlled diabetes mellitus; neuromuscular, musculoskeletal, or mucocutaneous conditions requiring frequent treatment; seizure disorders requiring treatment; ongoing infection or other medical conditions requiring frequent medical management; or pharmacologic or surgical treatment that, in the opinion of the Investigator or the Sponsor, makes the subject unsuitable for study participation
8. History of HCC
9. A history of malignancy other than HCC unless the subject's malignancy has been in complete remission off chemotherapy and without additional medical or surgical interventions during the 3 years before Screening
10. History or presence at Screening of electrocardiogram (ECG) abnormalities deemed clinically significant in the opinion of the Investigator.
11. History of hypersensitivity or idiosyncratic reaction to any components or excipients of the investigational drug or PBO formulation
12. History of any significant food or drug-related allergic reactions such as, anaphylaxis or Stevens-Johnson syndrome

13. The following exclusionary laboratory results at the Screening and Baseline visit:
- Platelet count  $<100,000/\text{mm}^3$
  - Albumin  $<$ lower limit of normal
  - Total bilirubin  $>1.2 \times$  upper limit of normal (ULN) unless known Gilbert's syndrome; subjects with Gilbert's syndrome are eligible for study participation if the direct bilirubin is within the normal range
  - Direct bilirubin  $>1.2 \times$  ULN
  - ALT  $>10 \times$  ULN
  - Serum alpha fetoprotein (AFP)  $\geq 100$  ng/mL. If AFP at Screening is  $>$ ULN but  $<100$  ng/mL, the subject is eligible if a hepatic imaging study prior to initiation of study drug reveals no lesions indicative of possible HCC.
  - International Normalized Ratio  $>1.5 \times$  ULN
  - GFR  $<50$  mL/min/1.73 m^2 by CKD-EPI equation ([Levey 2009](#))
  - Any other laboratory abnormality deemed clinically significant by the Sponsor or the Investigator
14. Subjects receiving prohibited concomitant medications, grapefruit juice, or prohibited herbal/over-the-counter medications ([Section 6.4.1](#)) within 7 days or 5 half-lives (if known), whichever is longer, prior to administration of the first dose of study drug and for the duration of the study period.
15. Participation in another clinical study of a drug or device whereby the last investigational drug/device administration is within 60 days or 5 half-lives prior to the first study drug administration, whichever is longer. However, subjects receiving any prior investigational therapy for HBV, will be excluded.
16. Subjects who have received, in the previous 4 weeks, a treatment likely to alter the immune response (intravenous immunoglobulins, blood-derived products, or high-dose steroids, or other immunosuppressants).

## **6. INVESTIGATIONAL MEDICAL PRODUCTS**

### **6.1. Randomization, Blinding and Treatment Codes**

#### **6.1.1. Randomization**

Randomization of eligible subjects to their respective treatment assignments will be performed centrally using an Interactive Response Technology (IRT) system. Following successful completion of Screening assessments and confirmation of subject eligibility, site personnel will enter the subject specific information in the IRT system and receive a subject number at the Screening visit. Upon confirmation of subject eligibility on Day 1, the IRT system will assign eligible subjects in a 1:1 ratio to receive either 300 mg ABI-H0731+NrtI for 96 weeks (n=20) or PBO+NrtI for 48 weeks followed by 300 mg ABI-H0731+NrtI for 48 weeks (n=20). Individual treatment assignments will be stratified by the concurrent NrtI administered (ie, ETV versus TDF or TAF) and HBV DNA (HBV DNA  $\geq$ 500 IU/mL versus <500 IU/mL). The study will enroll approximately 75% subjects receiving ETV. Additional information on the use of the IRT is provided in the IRT user manual.

#### **6.1.2. Blinding**

Study subjects, Investigators and other site personnel administering the study drug, performing the clinical assessments and handling data on the study subjects, will be blinded to individual subject treatments assignments (ie, PBO+NrtI or ABI-H0731+NrtI) throughout the duration of the study. To support maintenance of the study blind, HBV pgRNA results will not be provided to the study subjects, Investigators or other site personnel until completion of the study.

A limited internal Sponsor team will be unblinded to individual subjects' treatment assignments throughout the study to ensure timely analysis of any emergent safety/tolerability issues, and completion of the prespecified safety data reviews. The unblinded individuals will be identified in the Statistical Analysis Plan (SAP) along with their specific roles and responsibilities. All other Sponsor personnel will remain blinded until completion of the study. The contract research organization's (CRO's) Medical Monitor may be unblinded to individual subjects' treatment assignments where required for assessment of emergent safety/tolerability issues.

#### **6.1.3. Unblinding in Emergency Situations**

Requests can be made to unblind an individual study subject for emergencies or urgent situations. Prior to unblinding, and if the situation permits, the Investigator should first contact the Sponsor and/or authorized Medical Monitor to discuss the case. However, the final decision whether to unblind a subject will be the Investigator's decision, and the Investigator need not wait for the unblinding permission to be granted by the Sponsor/CRO Medical Monitor in emergency situations where identification of the individual treatment assignment is required for the immediate medical management of the subject. Access to the unblinded treatment assignment should be limited to the minimum number of people required for emergent management of the subject. The actual treatment assignment must not be disclosed to the subject and/or other study personnel, including site monitors and office staff; nor should there be any written or verbal disclosure of the code in the subject's study documents.

The request for unblinding should include the protocol number, site number, subject number, treating Investigator's contact info, a detailed reason for the unblinding, and date the information is needed. All

key correspondence between the requestor and Sponsor or CRO Medical Monitor should be saved in the Trial Master File.

The IRT system will be used as the unblinding tool. In the event that an individual subject's treatment assignment is unblinded, the date and reason that the blind was broken must be recorded in the source documentation. Any treatment assignments that are unblinded must be immediately reported to the CRO Medical Monitor and the Sponsor. Code-break IRT access is given to the Investigator/designated person at the site and to the designated Medical Monitor(s) for the study.

Following unblinding, the subject will discontinue ABI-H0731 or matching PBO and continue with the study follow-up assessments.

## **6.2. Description and Handling of ABI-H0731 and Matching Placebo (Investigational Medicinal Product)**

The investigational medicinal products (IMPs) to be used in this study are ABI-H0731 and matching PBO.

### **6.2.1. Formulation**

The drug product is a tablet containing ABI-H0731 formulated in a solid dispersion which is produced by spray drying a solution of ABI-H0731 with an inert polymer HPMCP HP-55. This spray-dried dispersion has been mixed with standard pharmaceutical excipients, such as microcrystalline cellulose, calcium phosphate, croscarmellose sodium, and magnesium stearate, and compressed into a tablet containing approximately 100 mg of ABI-H0731, manufactured according to Good Manufacturing Practices (GMP).

### **6.2.2. Packaging and Labeling**

ABI-H0731 tablets and matching PBO tablets are packaged in high density polyethylene bottles fitted with child-resistant screw caps, induction sealed and shipped to sites under ambient conditions.

The IMP will be labelled in accordance with US Food and Drug Administration (FDA) requirements and European Union GMP Annex 13, Investigational Medicinal Products. Additional local labelling requirements in countries of study conduct will be incorporated in the IMP label(s).

### **6.2.3. Storage and Handling**

Bottled drug product at the study site should be stored at controlled room temperature (15 °C to 30 °C [59 °F to 86 °F]) in a secure, locked location at the sites, accessible only to study personnel.

## **6.3. Description and Handling of NrtI (Non-Investigational Medicinal Product)**

All subjects will enter the study receiving standard-of-care NrtI monotherapy of either ETV, TDF or TAF. The NrtIs used by subjects in this study are designated as non-investigational medicinal products (NIMP) (background therapy). Subjects taking a NrtI other than ETV, TDF, or TAF are excluded from study participation. Subjects will continue to administer their same standard-of-care NrtI used prior to and during Screening and continue for the entire duration of the study including follow-up. If a subject's access to concurrent standard of care NrtI therapy should change while on-study, then the Investigator should first contact the Sponsor and/or authorized Medical Monitor to discuss the case-

Details describing the packaging, labelling, storage and handling of the NrtI are described in the respective package insert.

## **6.4. Prior and Concomitant Medications**

A concomitant medication is defined as any prescription or over-the-counter preparation, including vitamins, medications, vaccinations, herbal preparations, and supplements, that is administered to a study subject during the conduct of the clinical trial. For randomized subjects, concomitant medications are discouraged, unless they are prescribed by the Investigator for treatment of an emergent medical event occurring during the course of the study. No concomitant procedures will be performed during the study unless approved by the Investigator.

All concomitant medications taken from the date the Informed Consent Form (ICF) is signed, through end of the study (completion of the follow-up period) must be recorded in the subject's source documentation. This information should include the name of the medication or treatment, the dose and regimen, the start and stop dates, and the indication for which the concomitant medication was administered.

### **6.4.1. Prohibited Concomitant Therapy**

Systemic (oral, injectable, or implanted) hormonal birth control is not permitted as an acceptable means of contraception for female subjects of child-bearing potential. Additional details on acceptable means of contraception are provided in [Appendix 5](#).

Since ABI-H0731 is a weak inhibitor of cytochrome P450 (CYP) 2C9, concomitant use with narrow index CYP2C9 substrates such as warfarin and phenytoin are prohibited. Use of other CYP2C9 substrates should be avoided. Those taking sulfonylureas for controlled diabetes mellitus should monitor blood sugar levels and adjust dosage as appropriate. To the extent possible, other medications with narrow therapeutic indices should be avoided.

The route of elimination in humans is not fully understood so inhibitors and inducers of CYP3A4 should be avoided. Refer to [Appendix 5](#) for details on prohibited CYP2C9 substrates as well as inhibitors and inducers of CYP3A4.

Provisions regarding concomitant medications described in the respective NrtI product labeling must also be followed during the study through the end of the follow up period.

The designated Medical Monitor may be consulted for any questions regarding acceptable or prohibited concomitant medication use during the study. As previously described, concomitant medications, over-the-counter medications, and supplements must be recorded in the subject's source documentation.

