### **Definition of Female Subjects of Childbearing Potential**

A female subject is considered of childbearing potential following menarche and until becoming postmenopausal unless permanently sterile (see below).

If fertility is unclear (eg, amenorrhea in adolescents or athletes) and a menstrual cycle cannot be confirmed before first dose of study drug, additional evaluation should be considered.

Female subjects in the following categories are not considered of childbearing potential

- Premenopausal with one of the following:
  - Documented hysterectomy
  - Documented bilateral salpingectomy
  - Documented bilateral oophorectomy
- Postmenopausal: A postmenopausal state is defined as no menses for 12 months without an alternative medical cause.
- A high FSH level in the postmenopausal range may be used to confirm a postmenopausal state in women not using hormonal contraception or hormonal replacement therapy (HRT). However, in the absence of 12 months of amenorrhea, confirmation with more than 1 FSH measurement is required.
- Females on HRT and whose menopausal status is in doubt will be required to use one of the non-estrogen hormonal highly effective contraception methods if they wish to continue their HRT during the study. Otherwise, they must discontinue HRT to allow confirmation of postmenopausal status before study enrollment.

For individuals with permanent infertility due to an alternate medical cause other than the above, (eg, Müllerian agenesis, androgen insensitivity), Investigator discretion should be applied to determining study entry.

Documentation to determine childbearing potential can come from the site personnel's review of the subject's medical records, medical examination, or medical history interview.

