### **Contraceptive Requirements**

The drug-drug interaction (DDI) study with ABI-H0731 and oral contraceptive has not been completed, and therefore, oral contraceptives are not acceptable as a form of effective birth control.

Female subjects of childbearing potential (defined above) must agree to use dual effective birth control methods for the duration of the study and follow-up. Effective birth control methods include male or female condom (may not be used together due to increased risk of breakage), vasectomy, tubal

Protocol Amendment 1 ABI-H0731-205  
08 September 2020

---

sterilization, intrauterine device (IUD), diaphragm, or cervical cap. Note that the DDI of ABI-H0731, and systemic (oral/injectable) hormonal birth control has not been assessed and so systemic hormonal birth control is not considered effective birth control method for female subjects for the purposes of this study. Female subjects must have a negative serum pregnancy test at Screening and a negative urine pregnancy test prior to receiving the first dose of study drug at Baseline (Day 1).

All male subjects must agree to use dual effective birth control methods with their female partners if they are of childbearing potential for the duration of the study and follow-up. In this case, effective birth control methods include systemic (oral/injectable) hormonal birth control, male or female condom (may not be used together due to increased risk of breakage), vasectomy, tubal sterilization, IUD, diaphragm, or cervical cap.

Male subjects must avoid sperm donation from the time of the first dose of study drug and throughout the study period, and for at least 30 days after administration of the last dose of study drug.

Protocol Amendment 1 ABI-H0731-205  
08 September 2020

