## APPENDIX 5 CYTOCHROME P450 3A4 INHIBITORS AND INDUCERS AND CYP2C9 SUBSTRATES

The following drugs are known inhibitors of CYP3A4 and CYP2C9 substrates and should be avoided when taking ABI-H0731:

CYP3A4 Inhibitors	
HIV antivirals	indinavir, nelfinavir, ritonavir, saquinavir
Other	clarithromycin, itraconazole, ketoconazole, nefazodone, saquinavir, idelalisib, ribociclib, telithromycin, aprepitant, erythromycin, fluconazole, grapefruit juice, netupitant/palonosetron, verapamil, diltiazem, voriconazole, cimetidine, amiodarone, NOT azithromycin, chloramphenicol, boceprevir, ciprofloxacin, delaviridine, diethyl-dithiocarbamate, fluvoxamine, gestodene, imatinib, mibefradil, mifepristone, norfloxacin, norfluoxetine, starfruit, telaprevir, voriconazole

The following drugs are known substrates of CYP2C9:

CYP2C9 Substrates	
Narrow therapeutic index substrates that are prohibited while taking ABI-H0731	Warfarin, phenytoin
Substrates that should be avoided while taking ABI-H0731	Amitriptyline, capecitabine, celecoxib, clopidogrel, diclofenac, doxepin, fluoxetine, Fluvastatin, glibenclamide, glimepiride, glipizide, glyburide, ibuprofen, irbesartan, lesinurad, lornoxicam, losartan, meloxicam, nateglinide, piroxicam, rosiglitazone, naproxen, suprofen, tamoxifen, tolbutamide, torsemide, valproic acid, venlafaxine, voriconazole, zakirlukast

The following drugs are known inducers of CYP3A4 and should be avoided when taking ABI-H0731:

CYP3A4 Inducers	
	Barbiturates, brigatinib, carbamazepine, efavirenz, enzalutamide, glucocorticoids, modafinil, nevirapine, oxcarbazepine, phenobarbital, phenytoin, pioglitazone, rifabutin, rifampin, st. john's wort, troglitazone

Source: The Flockhart Table. <http://medicine.iupui.edu/clinpharm/ddis/main-table#> (Accessed 6 March 2020).  
Abbreviations: CYP=cytochrome P450.

Protocol Amendment 1 ABI-H0731-205  
08 September 2020

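### Exclusion 14 relies on a list of prohibited products that Section 6.4.1 and Appendix 5 do not define consistently, and the Appendix 4 HRT bullet conflicts with the rule on hormonal contraception

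*Combined protocol and SAP*

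**What the plan says.** **Eligibility.** Exclusion 14 (protocol Section 5.3) covers "Subjects receiving prohibited concomitant medications, grapefruit juice, or prohibited herbal/over-the-counter medications", with a washout of 7 days or 5 half-lives, whichever is longer, and continues for the whole study. Section 5.3 cites Section 6.4.1, and the Synopsis version says outright that 6.4.1 supplies the definition.

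**The list.** Section 6.4.1 is headed as prohibited therapy. It states that "concomitant use with narrow index CYP2C9 substrates such as warfarin and phenytoin are prohibited". For other CYP2C9 substrates, and for CYP3A4 inhibitors and inducers, it uses the weaker advice to avoid. On one class it adds: "Those taking sulfonylureas for controlled diabetes mellitus should monitor blood sugar levels and adjust dosage as appropriate". It then sends the reader to Appendix 5 for "details on prohibited CYP2C9 substrates as well as inhibitors and inducers of CYP3A4".

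**Appendix 5.** One CYP2C9 row is marked prohibited (warfarin, phenytoin). The other is labelled "Substrates that should be avoided while taking ABI-H0731" and includes "glibenclamide, glimepiride, glipizide, glyburide", with tolbutamide further along. The CYP3A4 inhibitors and inducers are all marked as to be avoided.

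**Contraception.** Section 6.4.1 does not accept systemic hormonal methods for females of child-bearing potential and refers to Appendix 5 for details. In Appendix 4, under the contraceptive requirements, "systemic hormonal birth control is not considered effective birth control method for female subjects". In the same appendix, women on HRT whose menopausal status is uncertain, and who want to stay on HRT, "will be required to use one of the non-estrogen hormonal highly effective contraception methods".

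**The concern.** Exclusion 14 works only if a site can look up a product and find one answer. The word that triggers exclusion is *prohibited*, and the section that is meant to define it applies that word to one group, gives softer advice for the rest, and then uses a cross-reference that can be read as extending the stronger word to everything in Appendix 5. Two careful sites could reach opposite decisions on the same candidate and could differ on whether a washout is needed.

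This matters because Section 7.1 allows no protocol waivers, about 10 centers were planned (Section 4.1), and consulting the Medical Monitor is optional. The contraception wording matters because Appendix 4 states that embryofetal development studies of ABI-H0731 have not been done. At stake are consistent eligibility decisions, consistent classification of deviations, and subject safety.

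**Working it through.** The protocol gives no figure on this point, so the check is a comparison of texts.

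**Step 1. Status of the same product in three places.**

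| Product | Section 6.4.1 | Appendix 5 | Exclusion 14 |
|---|---|---|---|
| Warfarin | prohibited | prohibited | barred |
| Phenytoin | prohibited | prohibited (CYP2C9 table) and avoid (CYP3A4 inducer table) | barred |
| Grapefruit juice | not named; its class is avoid | avoid | barred by name |
| Rifampin | not named; its class is avoid | avoid | depends on the reading |
| St John's wort | not named; its class is avoid | avoid | depends on the reading; no prohibited herbal list exists |
| Ibuprofen | not named; its class is avoid | avoid | depends on the reading |
| Glipizide | use foreseen, with a condition | avoid, no condition | not barred on the literal text |

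Only warfarin has the same status throughout. Phenytoin carries two labels inside Appendix 5. Grapefruit juice is graded more strictly in Exclusion 14 than in Appendix 5.

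**Step 2. The readings available to a site.**
- *Narrow:* only what 6.4.1 directly calls prohibited counts, that is, narrow-index CYP2C9 substrates, plus grapefruit juice, which Exclusion 14 names itself. The group is open-ended because warfarin and phenytoin are given as examples.
- *Broad:* the heading of 6.4.1 and its pointer make all of Appendix 5 the prohibited list.
- The pointer does not settle the matter. Its adjective may govern the CYP2C9 substrates alone or the CYP3A4 drugs as well, and within CYP2C9 it may mean the prohibited row or the whole table.

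**Step 3. Apply both readings.** Take a candidate still on rifampin or St John's wort inside the 7-day window. On the narrow reading Exclusion 14 is not triggered and no washout is required. On the broad reading the candidate is excluded unless the product is stopped in time. For St John's wort there is a further gap: Exclusion 14 speaks of prohibited herbal products, 6.4.1 names none, and the product appears only in Appendix 5, as one to avoid.

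**Step 4. Sulfonylureas.** Section 6.4.1 first advises avoiding other CYP2C9 substrates and then sets a condition for people who are taking a sulfonylurea. Appendix 5 places five sulfonylurea names in the avoid row without that condition. A site that consults only the appendix would not know the condition exists.

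**Step 5. Contraception.** The general rules in 6.4.1 and Appendix 4 agree: systemic hormonal methods do not count for female subjects of child-bearing potential. Three things do not fit.
- The HRT bullet calls for a non-estrogen hormonal method, whereas the Appendix 4 list of effective methods for female subjects names no hormonal method and requires two methods.
- That bullet sits among the categories of women not considered of child-bearing potential, yet it demands contraception because that status is in doubt. A site cannot tell whether the general rule applies.
- The pointer in 6.4.1 goes to the CYP tables in Appendix 5; the contraception text is in Appendix 4. Appendix 4 also omits implants, which 6.4.1 names.

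**The case against.** The strongest reply is that these are drafting slips with safeguards around them. Exclusion 7 gives the Investigator and Sponsor discretion over ongoing infection and treated seizure disorders, which would catch some users of rifampin or carbamazepine. Section 6.4 discourages concomitant medication after randomization. The Medical Monitor may be consulted. Inclusions 4 and 9 cite Appendix 4 correctly. A woman on HRT may stop it instead, and because Appendix 4 accepts IUDs without specifying type, a method that satisfies both texts may exist. All of this stands, and it is why sites *could*, not *will*, differ. But discretion and optional consultation do not supply the missing definition.

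Several stronger inferences are tempting and are not supported:
- **That 6.4.1 contradicts Exclusion 14.** It does not; Exclusion 14 defers to 6.4.1. The fault is an unclear list.
- **That the sulfonylurea sentence breaches a ban.** Neither passage bans the class. Advice to avoid followed by a condition reads as a general caution with an exception. What remains is that Appendix 5 omits the exception.
- **That a user of an HIV antiviral such as ritonavir could slip in.** Exclusion 3 removes HIV co-infection, so this is a poor example.
- **That a count of drugs sizes the problem.** Appendix 5 has 35 inhibitors, 30 avoid-row substrates, 16 inducers and 2 prohibited drugs: 35 + 30 + 16 + 2 = 83, less 2 duplicates (voriconazole, phenytoin) = 81 entries. This counts list items, not subjects. Nor does 1/20 = 5 percentage points help, since it is the weight of any one subject in an arm of 20.
- **That interactions would bias the comparison because only Group 1 takes active drug before Week 48.** An event caused by ABI-H0731 acting on another drug is a true effect of ABI-H0731, which the placebo arm is there to reveal. The protocol calls the CYP2C9 inhibition weak, says elimination is not fully understood, and gives no interaction size.

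**Conclusion.** The point holds as a defect of wording with consequences for eligibility and safety. The prohibited list on which Exclusion 14 depends cannot be applied consistently as written, and the HRT bullet cannot be squared with the contraceptive rule without guesswork. The passages must be reconciled.

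Its size cannot be stated as a number. The documents give neither the frequency of use of the listed products nor the strength of any interaction. A reader might infer a distorted treatment comparison, but there is none to distort: SAP Section 1 reports early termination with 2 subjects randomized, Section 3 provides listings only, and Sections 6 and 8 drop formal efficacy and PK analysis. What remains is classifying concomitant medication and deviations for those two subjects, and any reuse of this text in another protocol.

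The conclusion assumes that sites worked from the protocol text alone. The manuals it cites were not available here and might contain a clearer list.

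**What to change.** - Give each Appendix 5 class one status, with identical wording in Section 6.4.1, Appendix 5 and Exclusion 14 (Section 5.3 and Synopsis). Resolve the double label on phenytoin and the different grading of grapefruit juice.
- State which herbal and over-the-counter products Exclusion 14 covers, or refer to the exact table.
- Say whether the washout applies to products marked as to be avoided.
- Carry one sulfonylurea statement in both 6.4.1 and Appendix 5.
- Reconcile the Appendix 4 HRT bullet with 6.4.1 and with the two-method rule, and treat implants the same way in both places.
- Correct the contraception pointer in 6.4.1 to Appendix 4.

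Which status each class receives, and what the HRT bullet should require, is for the sponsor's clinical pharmacology and medical leads.

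The cost is amendment wording and a short site memo; some candidates might become clearly ineligible. With enrolment over, the practical step is to record in the synoptic report how the two subjects' concomitant medications were classified, and to correct the text before it is reused.
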